# Hypothesis: High school staff in the PLANTS arm will have high intervention demand (≥75% of enrolled participants will adhere to the PLANTS intervention).

Intervention Demand will be a variable ranging from 0-100%. Investigators assess PLANTS adherence, which is a composite variable ranging from 0% to 100%, comprised of 55% for module completion (based on the number of completed items divided by the total number of items offered) and 45% for Live Zoom Event attendance (where each event is 15%). These proportions are based on approximate time allocations.

Adherence is reflected by a score of 100%. We will calculate an overall adherence rate among PLANTS participants with a 95% confidence interval.

# PLANTS Pilot Trial Version 1.0 Protocol STUDY21080178 2024.04.05 Hypothesis: High school staff participants in the PLANTS arm will report pre-post improvements in active- empathic listening, self-efficacy for supporting, affirming, and protecting sexual and gender minority youths, and positive bystander intervention behaviors for bullying.

To examine the pre-post changes in high school staff outcomes, investigators will first use descriptive statistics, such as means and percentages at each timepoint within arms. To test for within-arm statistical significance, investigators will use linear mixed models for continuous outcomes and generalized linear mixed models for binary outcomes, which account for within-school and within-person clustering using random effects. Investigators will estimate the intraclass correlations for within-school and within-person effects. These models will adjust for school size (*a priori* design variable).

Hypothesis: Participants in PLANTS will report greater active-empathic listening, greater self-efficacy for supporting, affirming, and protecting SGMY, and greater positive bystander intervention behaviors for bullying in follow-up surveys than participants in the active control arm.

We will use linear mixed models for continuous outcomes and generalized linear mixed models for binary outcomes—which account for within-school and within-person clustering effects (using random effects). We will estimate the intraclass correlations for within-school and within-person effects. Regression models will include a fixed term for school size (a priori design variable), intervention group (intervention or control), time (baseline or follow-up), and the interaction of intervention group × time (our variable of interest). The test of intervention effects on secondary outcomes will be primarily based on intent-to-treat estimates. We will estimate perprotocol effects in secondary models. If there are differences in potential confounders by intervention group, we will adjust for them in secondary multivariable analyses.

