# PLANTS Pilot Trial Version 1.0 Protocol STUDY21080178 2024.04.05 risk factors (e.g., bullying victimization) and more protective factors (e.g., school-based adult support), which will in turn reduce SGMY's substance use and mental health problems.

#### Rationale for the Clinical Trial

The primary aim of this clinical trial is to rigorously test the acceptability, usability, appropriateness, and feasibility of the PLANTS intervention using a 2-armed cluster-randomized controlled trial. We will also examine the efficacy of intervention in improving high school staff outcomes as well as implementation and safety outcomes related to the intervention and trial. Results from this pilot trial will provide necessary information to conduct a fully powered trial of the efficacy of PLANTS for reducing the ultimate health outcome of SGMY alcohol use.

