# 4 STUDY DESIGN

# 4.1 Overall Design

This is a two-armed cluster-randomized controlled pilot trial of the PLANTS intervention versus an active control group, EMAILS (E-learning to Maximize Academic Inclusion of LGBTQ+ Students). The single study site is the University of Pittsburgh. The primary objective is to assess the acceptability, usability, appropriateness, and feasibility of the PLANTS intervention. We hypothesize that high school staff will rate the PLANTS intervention as having high acceptability, usability, appropriateness, and feasibility in the follow-up survey.

The secondary objectives are to examine the extent to which the PLANTS course and trial successfully implemented and safe for high school staff and schools. We will also evaluate the extent to which, among high school staff participants in the PLANTS arm, they report pre-post improvements in active-empathic listening, self-efficacy for supporting, affirming, and protecting sexual and gender minority youths, and positive bystander intervention behaviors for bullying. We will also assess the extent to which, among high school staff, the PLANTS intervention is more efficacious in improving active-empathic listening, self-efficacy for supporting, and positive bystander intervention behaviors for bullying than an email intervention of publicly available resources. We hypothesize that participants in PLANTS will report greater active-empathic listening, greater self-efficacy for supporting, affirming, and protecting SGMY, and greater positive bystander intervention behaviors in the active control arm.

We will randomize schools in an equal 1:1 ratio, stratified by large versus small schools, into intervention or active control conditions. We will use block randomization with block sizes of 2, which will be stratified by large schools versus not, where large is ≥1000 students. We use block size of 2 because there are only 4 schools in this pilot trial. [name] (PI) will use Stata (ralloc command) to generate the randomization list, which will be entered into REDCap using the randomization module. Because this is a cluster randomized trial, we will randomize schools after they are determined to have met all the eligibility requirements and they officially enroll in the study. Upon school enrollment, a research assistant will be responsible for entering the school into the REDCap database and hitting the "randomize" button. Randomization will occur prior to school staff

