# 9.4.7 Sub-Group Analyses

Primary endpoints will be analyzed based on gender, sexual identity, race/ethnicity, intrinsic religiosity, religious attendance, religious activity, and role in school. Average score differences will be estimated using mixed models with demographic characteristics as predictors and the primary endpoints as outcomes, adjusting for school clustering.

Secondary endpoints of PLANTS efficacy will be analyzed based on gender, sexual identity, race/ethnicity, intrinsic religiosity, religious attendance, religious activity, and role in school (i.e., effect modifiers). Multivariable models will contain the 3-way interaction term, all 2-way interaction terms, main effects of time, study arm, the potential effect modifier, and any variables that meaningfully differ between study arms at baseline. We will conduct both intent-to-treat and per-protocol analyses. A significant 3-way interaction suggests the presence of intervention effect heterogeneity. Following the approach of Kraemer to focus on effect size derivation, we will use Stata's postestimation "margins" command to probe the 3-way interaction terms to provide simpler meaningful results.

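### The within-arm school ICC promised in Section 9.4.3 is not identified when the two PLANTS schools differ in size, and no school ICC in this four-school pilot rests on more than 1 or 2 degrees of freedom

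*Combined protocol and SAP*

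**What the plan says.** Section 4.1 sets the number of clusters: "We use block size of 2 because there are only 4 schools in this pilot trial". Allocation is at school level: "We will randomize schools in an equal 1:1 ratio, stratified by large versus small schools, into intervention or active control conditions". The strata are binary, "stratified by large schools versus not, where large is ≥1000 students". The plan is therefore two schools per arm.

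For the pre-post hypothesis in PLANTS, Section 9.4.3 says: "To test for within-arm statistical significance, investigators will use linear mixed models for continuous outcomes", with generalized versions for binary outcomes, "which account for within-school and within-person clustering using random effects". It continues: "Investigators will estimate the intraclass correlations for within-school and within-person effects. These models will adjust for school size". No arm term is listed for this model.

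For the between-arm hypothesis, the same section lists fixed terms for school size, arm, time and arm by time, with random effects for school and person, and again promises both ICCs.

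Section 9.4.7 plans subgroup analyses of the primary endpoints, which Section 9.3 defines in PLANTS participants only: "Average score differences will be estimated using mixed models with demographic characteristics as predictors and the primary endpoints as outcomes, adjusting for school clustering". No size term is listed there.

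The plan names Stata but not ML or REML. It gives no fallback for a boundary or non-identified fit. It states no ICC value and no target precision for an ICC.

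**The concern.** A school variance is estimated from whatever differences between schools remain after the school-level fixed effects are removed. Two schools supply one such difference. A size term that distinguishes the two schools uses it up, so the same model cannot also yield a school ICC. Software may still print a number, and a reader could take a printed zero as evidence that staff responses do not cluster by school.

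The four-school model does not have this exact collinearity, but it keeps so little between-school information that its ICC is close to uninformative.

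The subgroup models in Section 9.4.7 raise a related but different problem. With no size term, the school effect is estimable, but from two schools only. When the variance estimate is zero, the fit becomes an ordinary regression and the demographic differences receive no school adjustment, although the plan says they will.

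**Working it through.** **Inputs.** Four schools, 1:1, stratified blocks of 2 (Section 4.1). Section 9.2 gives 86 staff per school, 50% consent and 75% follow-up: 86 × 0.50 = 43 enrolled per school, and 43 × 0.75 ≈ 32 at follow-up. The documents give no ICC, so 0.05 is an assumption, with 0.01 and 0.10 as a range.

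**The plan's own figures.** There is no stated ICC precision to reproduce. The planned sample sizes do reproduce: 344 × 0.5 × 0.5 × 0.75 = 64.5 (stated 65). The widths 2 × 1.96 × √(0.25/n) at n = 344, 172 and 86 are 0.106, 0.149 and 0.211 (stated 0.11, 0.15 and 0.21).

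**1. PLANTS-only pre-post model.** Let X hold the intercept, size and time, and Z the school dummies. The df for school variance are rank[X Z] − rank[X].

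| Schools in the model | rank X | rank[X Z] | df for school variance |
|---|---|---|---|
| Two PLANTS schools, one large and one small | 3 | 3 | 0 |
| Two PLANTS schools, continuous size, unequal | 3 | 3 | 0 |
| Two PLANTS schools, same stratum, binary size | 2 | 3 | 1 |
| Four schools, two large and two small | 5 | 6 | 1 |
| Four schools, all in one stratum, binary size | 4 | 6 | 2 |

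In the four-school rows, X also contains arm and arm by time.

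In the first case the REML log-likelihood is exactly flat: it changes by 0.0000 as school variance goes from 0 to 5. The ML log-likelihood falls steadily from zero and is the same whether the true ICC is 0.05 or 0.30. In simulated fits with one mixed-model package, ML always returned an ICC of 0.000 and REML a constant 0.500, whatever the data. Another package may print something else, but the data cannot determine it.

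**2. Four-school model.** At school level, intercept, arm and size leave 4 − 3 = 1 df. With m staff per school and one observation each, the between-school mean square ratio has expected scale λ = 1 + m × ICC/(1 − ICC). The REML/ANOVA estimate is zero when the ratio is below 1, so P(zero) = P(F(1,168) < 1/λ), where 168 = 4 × 42. For m = 43:

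- ICC 0.01: λ = 1.43, P(zero) = 0.595 (0.59 by simulation)
- ICC 0.05: λ = 1 + 43 × 0.05/0.95 = 3.26, P(zero) = 0.42
- ICC 0.10: λ = 5.78, P(zero) = 0.32

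Each 95% CI limit for the ICC is (F/q − 1)/(F/q − 1 + m), where q is the 97.5% point (5.115) for the lower limit and the 2.5% point (0.000985) for the upper. At F = 3.26, that is at an observed ICC of 0.05:

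- Lower: 3.26/5.115 = 0.64, below 1, so 0.
- Upper: 3.26/0.000985 ≈ 3313, giving 3312/(3312 + 43) = 0.99.

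At a true ICC of 0.05 the median CI is 0 to 0.97. At 0.01 and 0.10 it is 0 to 0.94 and 0 to 0.98.

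**3. Two same-stratum PLANTS schools, binary size.** With 1 df and m = 43, the median CI at a true ICC of 0.05 is again 0 to 0.97.

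**4. Section 9.4.7 primary-endpoint subgroup models.** Two schools, m = 32, so 2 × 31 = 62 within-school df, ignoring the demographic predictors:

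- ICC 0.05: λ = 1 + 32 × 0.05/0.95 = 2.68, P(zero) = 0.46
- ICC 0.10: λ = 4.56, P(zero) = 0.36

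**The case against.** **The ICC is a by-product.** It appears in no objective, endpoint or hypothesis, and no precision is claimed for it. This stands and limits the weight of the point. In a random-intercept model the person-level ICC within schools and the time and arm-by-time coefficients stay estimable. The primary analysis in Section 9.4.2 uses means and CIs and does not depend on any ICC.

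**The main trial could be under-sized.** A reader might infer this from Section 2.1: "Results from this pilot trial will provide necessary information to conduct a fully powered trial". The documents do not support it. That sentence goes on to a trial whose outcome is alcohol use among students, whereas these ICCs concern staff self-reports. Nowhere does the plan say a staff ICC will set a sample size.

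**The collinearity is conditional.** This stands. The large/small split is not given, nor whether size enters as binary or continuous. Two large and two small schools guarantee one of each in PLANTS. If all four share a stratum, binary size is constant. A 3/1 split could leave PLANTS with one school (no school ICC), two, or three (1 df with binary size). None of these cases gives a usable ICC.

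**A PLANTS-only fit is inferred.** It is the natural reading of a within-arm model with no arm term. If the contrast is instead taken from the four-school model, the 1-df result applies.

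**The 42% depends on the estimator.** With two observations per person and an assumed within-person correlation of 0.5 to 0.7, it is 38 to 40%. Under ML with one observation per person, it is about 73%. Hence roughly 40% under REML/ANOVA, and no estimator rescues the ICC.

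**Section 9.4.7 is a separate matter.** Agreed: it has no size term, so the collinearity does not apply. The calculation shows how often the adjustment disappears, not how much bias follows.

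**Conclusion.** The point holds as an error in a secondary analysis as written. If the within-arm model is fitted to PLANTS alone and its two schools differ on the size variable, the promised school ICC has 0 df and is not identified. This is algebra and needs no assumed ICC. If the two schools share a stratum and size is binary, the ICC has 1 df and a CI of about 0 to 0.97.

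The four-school ICC is computable on 1 df (2 if binary size is constant) but says almost nothing. On 1 df, with 43 staff per school and REML/ANOVA estimation, it is zero in roughly 40% of trials at an assumed ICC of 0.05, about 59% at 0.01 and 32% at 0.10.

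The two-school random effect in the Section 9.4.7 primary-endpoint models is estimated as zero in about 36 to 46% of trials (assumed ICC 0.10 to 0.05, 32 per school).

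A reader might also infer that the pre-post or between-arm comparisons cannot be estimated. They can. Which standard error or df their tests should use is a different question and is not decided here.

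**What to change.** 1. **Section 9.4.3, PLANTS-only pre-post models.** Replace the random school effect and the size term with a fixed school indicator, keeping the random person effect. Alternatively, take the PLANTS change as a contrast (time plus arm by time) from the four-school model. State which.
2. **Section 9.4.3, within-arm ICC.** Delete the school ICC from the within-arm analysis and keep the person-level ICC.
3. **Section 9.4.3, four-school model.** Report the school ICC only with its 95% CI, labelled descriptive, and name the estimator (ML or REML).
4. **Section 9.4.7, primary-endpoint subgroup models.** Use a fixed school indicator instead of a random school effect, so that demographic differences are always compared within school.

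The cost is SAP wording. No data collection or design feature changes. The pilot gives up a within-arm school ICC that it cannot deliver. The fixed indicator absorbs size, so no separate size coefficient is available within PLANTS.

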#### 9.2 Sample Size Determination

#### Primary Endpoints

To adequately evaluate the primary endpoints, we need precise estimates of acceptability, appropriateness, and feasibility. We calculated our sample size based on our primary outcomes, a 5% error rate, and best practices for feasibility studies. The median number of teachers at each MetroWest Region high school is n=86. With 4 schools in our sample, we anticipate inviting a total  $\geq$ 344 school staff to participate in the pilot study. Assuming 50% agree to participate, 50% of participants are in the PLANTS study arm, and 75% of PLANTS participants complete the follow-up survey (reduced n=65), we can estimate 95% CI widths  $\leq$ 0.33 for AIM, IAM, and (based on the largest upper CI limit of the AIM, IAM, and FIM standard deviations) and  $\leq$ 10.1 for SUS. Such precision levels are sufficient.

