# 9.4 Statistical Analyses

# 9.4.1 General Approach

With the ITT Analysis Population, we will calculate baseline descriptive statistics by study arm using means and standard deviations for continuous variables, and frequencies and percentages for categorical variables. We will test for differences in potential confounders between intervention and control arms using baseline staffand school-level data with Rao-Scott chi-square tests for categorical variables and linear mixed models (with a random effect for school) for continuous variables (models adjusting for the clustering of staff within schools). Secondary analyses will adjust for imbalances between arms. For previously validated scales, we will report

internal consistency via Cronbach's alpha for continuous scales. For newly created items, we will conduct exploratory factor analyses to examine the dimensions of our outcomes as well as internal consistency using baseline surveys. We will use the most recent version of Stata. All tests are two-tailed and  $\alpha$ =0.05. Given the small sample size and pilot nature of these analyses, we will not perform any corrections for multiple tests.

Regarding qualitative analyses, we will transcribe, de-identify, and quality check all data. We will perform qualitative analyses in Dedoose. We will use CFIR as a guiding framework. Two qualitative coders will independently read interviews and compare coding until they agree they are on the same page. Once the coders, we will create a final codebook with definitions, rules, and examples for each code. Two coders will then recode all data using the final codes. We will calculate inter-rater reliability (i.e., Kappa statistic) to examine code application between coders. Coders will discuss any discrepancies until they reach agreement; [name] will resolve disagreements. We will use either a qualitative descriptive coding approach (wherein we describe and count the number of code applications) or axial coding (wherein we combine inductive codes into broader categories to define emerging patterns or themes). We will identify and interpret patterns in the data using a thematic analytic approach.

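### With four schools, the Section 9.4.3 efficacy tests name no school-by-time effect or school-based degrees of freedom; read as random-intercept models, their standard errors count staff, not schools

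*Combined protocol and SAP*

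**What the plan says.** Four schools are randomised 1:1 in blocks of two (Sections 4.1 and 6.3), "which will be stratified by large schools versus not, where large is ≥1000 students". How the four divide between the size strata is not stated. Section 9.4.3 then sets two efficacy tests on staff outcomes measured at baseline and follow-up.

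- **Within the PLANTS arm:** "To test for within-arm statistical significance, investigators will use linear mixed models for continuous outcomes", with generalized linear mixed models for binary outcomes and random effects for school and person. "These models will adjust for school size". "Investigators will estimate the intraclass correlations for within-school and within-person effects".
- **Between arms:** the same family of models, "which account for within-school and within-person clustering effects (using random effects". "Regression models will include a fixed term for school size (a priori design variable", together with arm, time and their interaction, which is the term of interest.

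Section 9.4.1 states "All tests are two-tailed and" sets alpha at 0.05. It cites the pilot setting only to justify not correcting for multiple tests. Section 9.4.7 extends the efficacy models to three-way interactions and reads a significant one as a sign of effect heterogeneity. None of Sections 9.2, 9.4.1, 9.4.3 or 9.4.7 names a school-by-time effect, a degrees-of-freedom rule, a school-level test, or a limit to estimation only.

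**The concern.** Both tests concern change over time. A school random effect that shifts baseline and follow-up equally protects comparisons of level between schools, but not comparisons of change. If schools change by different amounts, the planned p-values and intervals overstate certainty, and a significant efficacy result could be one school moving for its own reasons.

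School-specific change is plausible here. Section 4.2 presents PLANTS as something implemented in schools as a whole, existing school programmes are recorded at baseline, and school-board reaction and censorship (Section 8.2) can act on a whole school. Section 2.1 says the pilot's results will inform a fully powered trial, so a spurious efficacy signal could mislead that step.

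**Working it through.** **Inputs from the plan.** Section 9.2 gives a median of 86 teachers per school, four schools, 50% participation, half of participants in PLANTS, and "75% of PLANTS participants complete the follow-up survey (reduced n=65". This reproduces: 86 × 4 = 344; × 0.5 = 172; × 0.5 = 86; × 0.75 = 64.5, rounded to 65. Over two schools that is about 32 completers each; the same is assumed for EMAILS. The plan states no power or precision for the two tests. Its nearest figures, the secondary-endpoint CI widths, also treat staff as independent: 2 × 1.96 × √(0.25/n) gives 0.106, 0.149 and 0.211 at n = 344, 172 and 86, against 0.11, 0.15 and 0.21 stated.

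**Why the intercepts drop out.** With two time points, a random-intercept linear model says outcome = school + person + size + arm + time + arm × time + error. Subtracting baseline from follow-up removes school, person, size and the arm main effect. What remains is time, arm × time and the difference of two errors, so the test becomes a comparison of staff change scores that ignores school.

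This was checked by fitting. In 200 REML fits with school size in the model (two schools per arm with 54 and 10 completers, ICC of change 0.05), the interaction estimate equalled the difference in mean changes to 2e-15. Its standard error averaged 1.00 times the one that ignores school, and 29.5% of fits rejected.

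**Size of the inflation.** Let ρ be the share of change-score variance lying between schools. The documents give no value, so 0 to 0.10 is assumed. With m completers in every school,

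actual level = 2 × [1 − Φ(1.96 / √(1 + (m − 1)ρ))].

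For example, at m = 32 and ρ = 0.02: 1 + 31 × 0.02 = 1.62, and 1.96/√1.62 = 1.54, giving 0.124. Simulation used 200,000 runs per cell, completers only:

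| ρ | 0 | 0.01 | 0.02 | 0.05 | 0.10 |
|---|---|---|---|---|---|
| Formula, 32 per school | 0.050 | 0.087 | 0.124 | 0.220 | 0.333 |
| Group × time, 32 per school | 0.052 | 0.090 | 0.129 | 0.227 | 0.350 |
| PLANTS pre-post, 32 per school | 0.054 | 0.093 | 0.131 | 0.230 | 0.350 |
| Group × time, 44 and 20 in each arm | 0.051 | 0.095 | 0.139 | 0.247 | 0.374 |
| Group × time, 54 and 10 in each arm | 0.052 | 0.108 | 0.162 | 0.294 | 0.425 |
| Group × time, 50 and 50 against 14 and 14 | 0.052 | 0.078 | 0.104 | 0.180 | 0.278 |

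The unequal layouts are illustrations; the documents do not give the school sizes.

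**School-level alternative.** Four school mean changes less intercept and arm leave 2 df (critical value 4.30). Keeping the size stratum leaves 1 df (12.71) if both strata contain schools. The 2-df test rejects in 5.0–5.1% of runs with equal schools, 2.9–4.8% at 54 and 10, and 5.0–5.8% at 50, 50 against 14, 14. It is conservative (1.3–3.6%) if the strata differ in change by an assumed 0.3 SD. The 1-df test gives 4.9–5.0% with equal schools and 3.7–4.8% at 54 and 10.

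**Interval width.** As written, 2 × 1.96 × √(2/64) = 0.69 SD of change. Simulated medians at ρ = 0.02 with equal schools are 1.61 SD on 2 df and 3.85 SD on 1 df. At 54 and 10 they are 2.01 and 4.80 SD, against 0.69 as written.

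**Within-arm model, if fitted to PLANTS alone.** With one large and one small school, intercept and size have rank 2, and adding school indicators leaves it at 2. Size is then aliased with school, and 0 df remain for the school variance. With both schools in one stratum the ranks are 1 and 2, leaving 1 df.

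**The case against.** The strongest reply is that this is a pilot: efficacy is secondary, the primary endpoints are descriptive, no power is claimed, and no progression rule uses these p-values. That limits the consequence. It does not remove the commitment to 0.05-level tests, and nothing in Section 9 confines them to estimation.

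A second reply is that much rests on reading and assumption. The text says random effects, not intercepts; intercepts are the natural reading because ICCs are promised for school and person only. A reader might also infer that the within-arm model is certainly unidentifiable. The documents do not support that. Section 9.4.3 never says the model is fitted to PLANTS staff alone, and a time contrast from a four-school model also fits the wording. The aliasing point is therefore conditional; the standard-error point stands either way.

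Third, exact cancellation is shown for linear outcomes with complete data, and the binary-outcome models were not simulated. Keeping staff with baseline data only changes little for linear outcomes: with 43 enrolled and 32 followed per school, ρ of 0.05 and assumed other variances, the error was about 23.5%, against 22.5% for completers.

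Finally, simply naming a school-by-time effect and a degrees-of-freedom method would also close the gap in the text. A blanket ban on significance statements is not required, since the 2-df interval holds roughly its level. What should stop is reading random-intercept p-values as efficacy evidence.

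**Conclusion.** The concern holds on the random-intercept reading and for linear outcomes: the two efficacy tests have standard errors driven by the number of staff, and their 5% level depends on an unstated assumption that schools do not differ in change. For both tests the error is about 5/9/13/23/35% at an assumed ICC of change of 0/0.01/0.02/0.05/0.10 with about 32 completers per school.

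A reader might infer that the true error is 35% or more. The documents do not support any one value: they give no ICC of change and no school sizes beyond a median, and at ICC 0 there is no inflation. Nor does the point reach the primary endpoints, which are means with confidence intervals in the PLANTS arm. For the within-arm ICC, the conclusion is conditional: under a PLANTS-only fit it is not identified if the two schools differ in size stratum, and rests on 1 df otherwise. This should be fixed in the SAP before analysis; it does not undermine the pilot's main aim.

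**What to change.** 1. In Section 9.4.3, base the between-arm efficacy contrast on the four school-level mean changes (changes in proportion for binary outcomes), with a 95% CI on school-based degrees of freedom. State which applies: 2 df with the size stratum left out, or 1 df if it is kept and both strata contain schools. Label the result preliminary, and do not interpret p-values from the random-intercept model as efficacy evidence.
2. Report PLANTS-arm pre-post change descriptively, by school. If a PLANTS-only model is fitted, drop school size from it and report no within-school ICC.
3. In Section 9.4.7, report the three-way interactions as exploratory estimates, not as significance-based evidence of heterogeneity.

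Only SAP wording changes, but there are two costs. The first is the wider intervals shown above. The second is that school-level mean changes use completers only, so staff with baseline data alone are lost relative to the all-enrolled intention-to-treat population in Section 9.3, on which Section 9.4.3 primarily relies. Keep the mixed-model point estimate, which uses all enrolled staff, as a supporting result.
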